4.3 End of Study Definition

The end of the study is when we have disseminated our results.

5 - Study Population

5.1 Inclusion Criteria

In order to be eligible for participation in **Aim 1 Control Arm** of this study, an individual must meet all of the following criteria:

- 1) aged 18 years or older
- 2) have capacity and willingness to provide consent

In order to be eligible for participation in **Aim 1 Intervention Arm** of this study, an individual must meet all of the following criteria:

- 1) aged 18 years or older
- 2) have capacity and willingness to provide consent

5.2 Exclusion Criteria

The exclusion criteria for both arms of Aim 1 include: 1) aged <18 years..

5.3 Vulnerable Populations

Adults who have used the food pantry are the target subject population because strategies to increase food pantry use may support food security and healthy eating behaviors among low-income adults, especially those designed to mitigate the high opportunity costs of waiting in line and stigma, such as digital ordering.

5.4 Lifestyle Considerations

Participants in the intervention arm will have to transition with their food pantry to online ordering after the baseline data collection period regardless of their participation in this research study. The change will be brought on “naturally” by the food pantry (not the NYULH researchers or specifically as part of this research study). There will be no other restrictions during any other parts of the study pertaining to lifestyle and/or diet.

5.5 Strategies for Recruitment and Retention

For Aim 1, we will choose the food pantry recruiting sites with help from Met Council Kosher Food Pantry Network. We will aim to select a control site that is similar to the intervention site based on food pantry characteristics (e.g., number of food pantry clients per week, primary language(s) spoken) and community-level characteristics (e.g., neighborhood poverty level).

IRB-approved NYULH study personnel will recruit participants in person at two Met Council food pantries and will obtain permission from the food pantries prior to in-person recruitment at their

facilities. We will have support from food pantry staff members in introducing the NYULH study to potential participants. The study personnel will be on-site at the food pantry to introduce the study to food pantry clients and answer questions. Food pantry staff will also be available to direct food pantry clients to the study personnel. The study team will provide the food pantry with a recruitment flyer to post and/or pass out informing clients of the study and directing them to scan a QR code for the consent form with more information about the study and access to the study team's contact information. After scanning the QR code, clients will first see a short paragraph ("Pre-Consent QR Code Copy") listing the eligibility requirements and explaining what the consent is, in addition to a note that they do not need to sign the form at that moment. After the short paragraph, they will be able to scroll down to view the consent.

We will collect names, phone numbers, email addresses, and mailing addresses from participants in a secure REDCap form to facilitate the follow-up data collection, which will be conducted virtually, and to distribute gift cards.

Screen failures include those who do not meet all of our inclusion criteria. Potential participants will be asked to answer one pre-screening question about their age to determine their eligibility. If they do not meet our inclusion criteria, these participants will be told by the Research Assistant, "Thank you for your time, but unfortunately, you are not eligible for this study." We will immediately discard information from screen failures and from individuals that do not provide consent to take part in this study. Re-screening is not applicable.

Prior to the follow-up period, the study team will provide the food pantry with a flyer and post-card-sized handouts to remind participants of the upcoming follow-up surveys.

Aim 2 will not involve any participant recruitment.

6 - Study Procedures

6.1 Aim 1

Data collection in the baseline period will occur during the two to four month period prior to the intervention month (months t-2 to t-4), and data collection in the follow-up period will occur during the two-to-four-month period after the transition to digital ordering (months t+2 to t+4). The months immediately preceding (t-1) and following (t+1) the intervention month will be omitted to account for potential uncertainty in the implementation of online ordering and to allow for sufficient time for food pantry clients to return to their food pantry, respectively.

For the baseline period/visit (in person), consent will take place in person at the food pantry and data collection will take place in person at the food pantry, with the option to take the survey online offered on a case-by-case basis. The following will occur for both arms:

- Participants will be asked to complete a survey about their food and nutrition security, diet behaviors, and frequency of food pantry visits. The survey will take about 10 minutes to complete. Survey responses will be collected using Qualtrics.
- We will administer the Behavioral Risk Factor Surveillance System (BRFSS) 6-item brief dietary assessment tool to participants in both arms to assess potential changes in fruit and vegetable intake (questions 9-14 in the survey attached in Research Navigator).
- Participants will be given a card with an appointment time of their choosing that falls within the follow-up period, which will also include the phone number for an IRB-approved NYULH study personnel that they can reach if they need to re-schedule.
- The food pantry items selected by participants will be documented in-person by the Research Assistant. It will take approximately 5 minutes for the Research Assistant to record the participants' food selections.

For the follow-up period/visit (virtual/phone):

- **Intervention Arm**
 - We will send follow-up reminders to participants via email and/or text, based on their preference.
 - Participants will be asked to complete a survey by phone about their food and nutrition security, diet behaviors, and frequency of food pantry visits. The survey will take approximately 20-25 minutes to complete. The survey will be administered by a member of the study team using the Follow-Up Survey Guide.
 - Data on participants' food selections will be gathered from the online ordering system. This data will be provided to the study team by Met Council. Participants will not need to wait for the Research Assistant to record their selections.

- **Control Arm**

- We will send follow-up reminders to participants via email and/or text, based on their preference.
- Participants will be asked to complete a survey by phone about their food and nutrition security, diet behaviors, and frequency of food pantry visits. The survey will take approximately 20-25 minutes to complete. The survey will be administered by a member of the study team using the Follow-Up Survey Guide.
- Since the follow-up data collection occurs virtually and the study team will not be on site at the food pantry to record food selections, we will instruct participants to take a photo of their selections at their next food pantry visit and email or text the photo to the research team, using the information on the appointment card. It will take approximately 5 minutes for participants to record their food selections and send them to the study team. If participants do not remember to take the photo, we will assess their recall of their selections during the follow-up conversation.

6.2 Aim 2

We will test for potential interaction effects at the individual-level by adding an interaction term for age group (18-61 vs. ≥ 62 years). We will use the data collected for Aim 1 to complete these analyses. No additional data will be collected for Aim 2.

7 - Participant Discontinuation/Withdrawal

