However, mistrust of emergency food resources may be disproportionately higher in immigrant (vs. non-immigrant) communities,²⁷ potentially due to stigma, fear of interaction with government representatives (e.g. NYPD, ICE), and other factors.²⁸ Evidence from qualitative research, for example, suggests that the stigma of waiting in public to be served reduces utilization and satisfaction of food pantries.²⁹ This was corroborated by a recent review study noting how food pantry clients describe reasonable wait times and an “easy process” as a cornerstones of good customer service in food pantry settings.³⁰ Thus, strategies to increase food pantry use may support food security and healthy eating behaviors among low-income adults, especially those designed to mitigating the high opportunity costs of waiting in line and stigma, such as digital ordering.

In the Parent Grant, we are leveraging the rapid growth in online grocery shopping and expansion of retailers accepting SNAP benefits in online transactions. The recent shift to online ordering in some food pantries affords a similar opportunity to support food security and a healthy diet among low-income adults, which we aim to leverage in this Administrative Supplement. Online ordering is available in a small number of food pantries across the U.S., such as the Portland Open Bible Community Pantry in Portland, OR and The Open Door in Essex County, MA, largely due to increases in food insecurity and social distancing measures during the COVID-19 pandemic.^{31,32} Anecdotal evidence suggests online ordering has contributed to increased food pantry use, potentially due to reductions in wait times, reduced stigmatization, and increases in self-efficacy and self-sufficiency.³³⁻³⁷ Increases in food pantry, in

turn, may improve food pantry clients' food security status and increase fruit and vegetable intake relative to a traditional distribution model,^{38,39} especially in combination with changes to food "pricing" (e.g., assigning foods with high nutritional value fewer points than less healthy food). To our knowledge, however, there have been no evaluations of the transition to online ordering in food pantries.

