8.4 Statistical Analyses

We will perform a linear regression to assess balance of demographic characteristics between conditions; because of the natural experiment design, these characteristics should be balanced. To assess differences in outcomes between study conditions, we will regress the outcome variable on indicator variables for the experimental conditions, with the control condition as the reference group; if necessary, we will also adjust for any respondent characteristics that may be unbalanced by condition. The design and methods proposed will achieve robust and unbiased results because random assignment to an intervention group or control group in the context of a natural experiment minimizes bias.

We will also test for potential interaction effects at the individual-level by adding an interaction term for age group (18-61 vs. ≥ 62 years). In the food pantry network, an average of 25% of clients served are above 61 years of age, so we will have adequate variation to assess potential interactions by age group. For assessing differences in the frequency of food pantry visits per month at the food pantry-level, we will also add an interaction term for age group, which the

food pantry network measures as child (<18 years), adult (18-61 years), and older adult (≥ 62 years).

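### Recruitment happens during visits and each arm is one pantry, yet baseline visit frequency is left out of the balance check and the pre-specified adjustment

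*Combined protocol and SAP*

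**What the plan says.** **Recruitment.** Section 5.5: "IRB-approved NYULH study personnel will recruit participants in person at two Met Council food pantries". It adds that "The study personnel will be on-site at the food pantry to introduce the study to food pantry clients and answer questions", and the flyer with the QR code also reaches clients through the pantry. Section 6.1 states that "consent will take place in person at the food pantry and data collection will take place in person at the food pantry", with an online survey only case by case. Eligibility turns on age alone: "Potential participants will be asked to answer one pre-screening question about their age to determine their eligibility". No client list, sampling frame or quota is described.

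**Arms.** Section 4.1 describes one control pantry and one pantry already due to change. Section 5.4 says the pantry, not the researchers, brings about the change. Section 5.5 aims for a similar control site, naming clients per week, language and neighbourhood poverty as examples.

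**Visit frequency.** At baseline, both arms "complete a survey about their food and nutrition security, diet behaviors, and frequency of food pantry visits" (section 6.1). Section 8.4.3 uses the individual-level answer as a secondary outcome. No other use is stated.

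**Analysis.** Sections 8.4 and 8.4.2 use a linear regression to "assess balance of demographic characteristics between conditions". They then regress the outcome on condition, adjusting for unbalanced respondent characteristics if necessary. Age group is the only planned effect modifier. Section 8.4.5 marks baseline descriptive analyses as not applicable.

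**Mechanism.** Section 2.1 argues that "strategies to increase food pantry use may support food security", and that shorter waits and less stigma may raise use.

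**The concern.** A client can enter only by being at the pantry when staff are there, so a frequent visitor has more chances than an occasional one. That has two consequences.

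1. **Between-arm comparison.** If the two pantries differ in how often their clients come, or in how intensively staff recruit, the two samples will differ in visit frequency. The plan's own reasoning ties visit frequency to food security. No randomisation protects against such a difference, and the only formal balance check does not look at it.
2. **Whom the estimate describes.** Section 5.3 names adults who have used the pantry as the target. If the effect varies with visit frequency, an average over recruits differs from an average over those clients.

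The first matters more, because it bears on whether the primary contrast can be read as an effect of online ordering.

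**Working it through.** **The plan's own figure.** Section 8.2 gives a difference of 0.5, SD 1.5, 90% power and 155 per condition. With a one-sided 5% test, 2 × 1.5² × (1.645 + 1.282)² / 0.5² = 154.2, so 155, which reproduces. A two-sided 5% test would need 190. Alpha and sidedness are not stated, which is a separate matter. 155/0.8 = 193.75, and the plan recruits 193. The standard error of the difference is 1.5 × √(2/155) = 0.17.

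**Inputs the documents lack.** They give no visit-frequency distribution, recruitment intensity or slope of food security score on visit frequency. Everything below is therefore assumption, shown as a range.

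**Step 1: how far apart could the samples be?** Let v be visits per month and q the chance of enrolling at each visit. Over the three-month window the chance of entry is 1 − (1 − q)^(3v), which becomes proportional to v as q becomes small. Mean monthly visits in the recruited sample:

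| Assumed client mix | Client mean | Proportional | q = 0.05 | q = 0.20 | q = 0.50 |
|---|---|---|---|---|---|
| A: 1/2/4 visits at 40/40/20% | 2.00 | 2.60 | 2.50 | 2.26 | 2.05 |
| B: 0.5/1/2/4 at 25% each | 1.88 | 2.83 | 2.71 | 2.39 | 2.04 |
| C: 0.33/1/2/4 at 30/30/20/20% | 1.60 | 2.71 | 2.57 | 2.23 | 1.86 |

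Two pantries with identical clients but different intensity differ as follows:
- q = 0.05 against q = 0.20: 2.50 − 2.26 = 0.24 (A), 2.71 − 2.39 = 0.32 (B), 2.57 − 2.23 = 0.34 (C).
- Proportional against q = 0.50, an extreme contrast: 0.55 (A), 0.79 (B), 0.85 (C).

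Different clienteles would add to or offset these gaps.

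**Step 2: what would that do to the contrast?** In an unadjusted regression the confounding is slope × difference in mean frequency. Take 0.1 point per monthly visit as a unit of account. The shift is 0.24 × 0.1 = 0.024 up to 0.85 × 0.1 = 0.085 points, or 5% to 17% of the planned 0.5. It scales linearly with the slope and has the slope's sign. To produce a full 0.5 by itself, the slope would have to be 0.5/0.85 = 0.59 to 0.5/0.24 = 2.1 points per monthly visit, which is steep against an SD of 1.5.

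**Step 3: whom does the estimate describe?** Assume half the clients come monthly (v = 1) and half weekly (v = 4), with an average effect over clients of 0.50. Proportional entry gives a monthly share of 1/(1 + 4) = 20%. With q = 0.10, entry chances are 0.271 and 0.718, a monthly share of 27%. With q = 0.25 they are 0.578 and 0.968, a share of 37%.

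| Assumed effect, monthly / weekly | Proportional | q = 0.10 | q = 0.25 |
|---|---|---|---|
| 0.7 / 0.3 | 0.38 | 0.41 | 0.45 |
| 0.5 / 0.5 | 0.50 | 0.50 | 0.50 |
| 0.3 / 0.7 | 0.62 | 0.59 | 0.55 |

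For example, 0.2 × 0.7 + 0.8 × 0.3 = 0.38, and 0.2 × 0.3 + 0.8 × 0.7 = 0.62. The direction follows entirely from which group is assumed to gain more. With no variation in the effect there is no shift.

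**The case against.** **What stands.** If both pantries recruit alike and have similar clients, over-representation is the same in each arm, and the contrast is sound for those recruited. Intensive recruitment over three months also makes over-representation small: with q = 0.50 the sample means are only 2% to 16% above the client means.

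**What stands in part.** The adjustment clause covers respondent characteristics generally, so it permits adjustment for visit frequency. It does not require it, and the check that would prompt it is demographic. Matching the control site on clients per week concerns volume; the same volume can come from many occasional or few regular visitors. An analysis of change from baseline would remove a stable difference linked to frequency, but section 8.4.2 does not state one for the primary outcome, and differing trends would remain.

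**Stronger readings that the documents do not support.**
- A reader might infer that frequent visitors have least to gain, so that the result is biased towards no effect. No section says so. Section 8.1 also expects less time spent accessing pantries, a saving that recurs at each visit and could favour frequent visitors.
- A reader might propose weighting by the inverse of visit frequency. That is right only if entry is strictly proportional to visits. In the 0.7/0.3 case with q = 0.25, such weights turn the 37/63 sample into about 70/30 and give 0.58 against a true 0.50, worse than the unweighted 0.45.
- A reader might take "We will immediately discard information from screen failures and from individuals that do not provide consent" to rule out describing participation. It protects individuals' information and does not forbid anonymous counts.

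**Conclusion.** The point holds as a gap in pre-specification. Entry depends on visit frequency, the arms are two non-randomised pantries, and a baseline variable central to the plan's mechanism has no place in the balance check or the fixed adjustment. A difference between pantries could pass undetected and confound the primary contrast.

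The documents do not show that such a difference exists. Under the assumed mixes and intensities, confounding is 0.02 to 0.09 points per 0.1 point of slope, of unknown sign. That is below the 0.17 standard error, but it does not shrink as the sample grows. It is unlikely to create the whole planned effect alone.

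The effect on whom the estimate describes is a matter of generalisability. It requires the effect to vary with frequency, and neither its direction nor its size can be settled from the documents.

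**What to change.** In sections 8.4 and 8.4.2:

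1. Add baseline monthly visit frequency to the balance table, shown by arm, and align section 8.4.5 with it.
2. Include baseline monthly visit frequency as a pre-specified covariate in every individual-level outcome model, whatever the balance table shows, with its functional form fixed in advance. Use the baseline value, because online ordering may itself change the follow-up value. For the visit-frequency outcome, state that this makes the model baseline-adjusted.
3. Optionally, report an exploratory interaction of baseline frequency with condition, labelled as such, to show whether the effect varies with frequency.

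**Cost.** A few lines of text and one term per model, with no new participant data. The trial was not sized for the interaction, so its interval may be wide.

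**Limits.** Self-reported frequency leaves some residual confounding. With one pantry per arm, no covariate can separate the pantry from the condition. Clients who made no visit in the window stay outside the sample; the pantry-level count in section 8.4.3 is aimed at new clients and does not correct the individual-level estimate.

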4.1 Overall Design

This research study includes two aims, though only Aim 1 involves human subjects. The duration of the study is 18 months.

In Aim 1, study team members will recruit low-income adults aged ≥ 18 years. Participants will be recruited from a food pantry that is not scheduled to transition to online ordering (control) and a food pantry that is scheduled to transition to online ordering after the baseline data collection period (intervention). Participants in both arms will complete an in-person survey. Potential participants who are not able to take the survey in-person, will be offered the option to take the survey online. To assess potential changes in fruit and vegetable intake, we will administer the Behavioral Risk Factor Surveillance System (BRFSS) 6-item brief dietary assessment tool (questions 9-14 in the survey attached in Research Navigator). A Research Assistant will record the food items they received in the relevant visit to the pantry. After the transition to online ordering at the intervention food pantry, participants will again complete the survey over the phone. The survey will be administered by a member of the study team using the Follow-Up Survey Guide. Participants in the control arm will record their food selections and send them to the study team during the phone call. Food selections for participants in the intervention arm will be accessible through the online ordering platform. The study team will then analyze the baseline and follow-up data for differences in outcomes between study conditions.

In Aim 2, we will test for potential interaction effects at the individual-level by adding an interaction term for age group (18-61 vs. ≥ 62 years).

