8.2 Sample Size Considerations

To calculate our sample size, we used estimates from a similar study that found that a food bank-delivered intervention (diabetes-appropriate food packages, text-based health education, and referrals to health care) resulted in a decrease in the mean food security score from 2.8 to 2.3, or a 6.3% decrease in the percentage of participants with low or very low food security status.⁴⁰ Based on this study, we assume the standard deviation of the food security score is 1.5 and estimate that 155 participants in each condition (total n=310) will provide 90% power to detect a 0.5 difference in food security score between experimental and control conditions. To account for a potential attrition rate of 20% in the follow-up period, we plan to recruit a total sample size of 193 participants per condition (total n=386).

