8.4.3 Analysis of the Secondary Endpoint(s)

The secondary outcomes for Aim 1 include changes in: 1) total cup-equivalents of fruits and vegetables selected per visit; 2) intake of fruits and vegetables; 3) time to obtain food from food pantry per visit (minutes); and 4) individual-level frequency of food pantry visits per month (n). To capture a potential increase in *new* clients visiting the food pantry due to the transition to online ordering, we will also measure changes in the frequency of food pantry visits per month at the food pantry-level (n).

The primary outcome for Aim 2 is the same as Aim 1 and measured using the same specifications, including number of fruits and vegetables selected per visit; total energy intake; intake of key food groups; time to obtain food from food pantry per visit; and individual-level and food pantry-level frequency of food pantry visits per month. For assessing differences in the frequency of food pantry visits per month at the food pantry-level, we will add an interaction term for age group, which the food pantry network measures as child (<18 years), adult (18-61 years), and older adult (≥ 62 years).

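### Follow-up food selections can reach the analysis without survey response in the intervention arm but need participant engagement in the control arm, and no analysis set stops this one-sided selection

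*Combined protocol and SAP*

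**What the plan says.** The outcome is the first-listed secondary outcome for Aim 1 in section 8.4.3, "total cup-equivalents of fruits and vegetables selected per visit", which that section frames as a change. Section 8.1 includes it in the second Aim 1 hypothesis, as follow-up versus baseline compared with control.

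At baseline, a Research Assistant records selections in person in both arms (section 6.1). At follow-up the routes differ:

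- **Intervention.** Section 6.1: "Data on participants' food selections will be gathered from the online ordering system", and "This data will be provided to the study team by Met Council". Section 4.1 agrees: "Food selections for participants in the intervention arm will be accessible through the online ordering platform". Neither section makes these data depend on completing the phone survey.
- **Control.** Section 6.1: "we will instruct participants to take a photo of their selections at their next food pantry visit and email or text the photo". The fallback is: "If participants do not remember to take the photo, we will assess their recall of their selections during the follow-up conversation". Section 4.1 describes it differently: "Participants in the control arm will record their food selections and send them to the study team during the phone call".

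Section 8.2 inflates the sample size "To account for a potential attrition rate of 20% in the follow-up period". Section 7.2 treats loss to follow-up as not applicable. Section 8.3 describes the population only as a sample of adults aged 18 or older. Section 8.4 regresses each outcome on condition, with no completer restriction and no method for missing follow-up values.

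**The concern.** The issue is who contributes a value, not how accurately it is measured. It would remain if order records, photos and recall were equally accurate.

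An intervention participant who cannot be reached but still orders has a follow-up value. A control participant who neither sends a photo nor takes the call has none. Equal attrition in the two arms does not cancel this, because non-response removes values from one side only. If people who disengage from the study choose produce differently from those who stay, part of the difference between arms would reflect that and not online ordering. The direction is unknown: if engaged participants select more produce, the bias works against the intervention; if they select less, it favours it. Adjusting for unbalanced characteristics, which section 8.4 allows, helps only so far as those characteristics explain non-response.

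**Working it through.** **Inputs from the plan.** 193 recruited per condition and 20% attrition (section 8.2). Check of the plan's figure: 155 / 0.8 = 193.75, against 193 stated, so the two agree to within rounding. In the other direction, 193 × 0.8 = 154.4 remain and 38.6 are lost per condition.

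**Assumptions not in the documents.**
- D, the gap in selections between non-responders and responders: 0.2, 0.3 or 0.5 SD.
- s, the share of intervention survey non-responders who still order in the follow-up window: 1 or 0.5.
- Control values come from the 154.4 who engage.
- Follow-up levels are compared without baseline, with a two-sided 5% test. The plan states neither alpha nor sidedness.
- Online ordering has no true effect.

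**Formulas.**
- Intervention values: n_I = 154.4 + 38.6s
- Share of these from non-responders: f = 38.6s / n_I
- Spurious difference: f × D
- Standard error in SD units: SE = √(1/n_I + 1/154.4)
- Rejection rate: 1 − Φ(1.96 − fD/SE) + Φ(−1.96 − fD/SE)

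**All non-responders still order (s = 1).** n_I = 193, f = 38.6/193 = 0.20, SE = 0.108.

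| D (SD) | Bias (SD) | Rejection rate |
|---|---|---|
| 0.2 | 0.04 | 6.6% |
| 0.3 | 0.06 | 8.6% |
| 0.5 | 0.10 | 15.3% |

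**Half still order (s = 0.5).** n_I = 173.7, f = 19.3/173.7 = 0.111, SE = 0.111.

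| D (SD) | Bias (SD) | Rejection rate |
|---|---|---|
| 0.2 | 0.022 | 5.5% |
| 0.3 | 0.033 | 6.0% |
| 0.5 | 0.056 | 7.9% |

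**Sensitivity to attrition.** With s = 1, attrition from 10% to 40% and D from 0.2 to 0.5 SD, the bias runs from 0.02 to 0.20 SD and the rejection rate from 5.4% to 39.8%.

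**Scale.** With 155 per condition, the difference detectable with 80% power at two-sided 5% is 2.80 × √(2/155) = 0.32 SD. A bias of 0.04 to 0.10 SD is roughly one eighth to one third of that.

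**If change from baseline is analysed.** A gap in selection level that is the same at baseline and follow-up subtracts out. D must then be read as the gap in change over time between responders and non-responders. The documents give no figure for it. It should be smaller than the gap in level so far as the level gap is stable.

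**Cost of a common set.** With 154.4 per arm, SE = √(2/154.4) = 0.114. The ratio is 0.114/0.108 = 1.05, so the interval is about 5% wider if all 38.6 (about 39) intervention records are set aside.

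**The case against.** A reader might infer that the plan commits to comparing all orderers with survey responders. The documents do not support that. No section says that orders of intervention participants who miss the call will be analysed, or that the regression uses every available value. Some text points towards one follow-up cohort: section 3.2 defines the Aim 1 endpoint as completed follow-up data collection, the Synopsis has all participants completing the follow-up survey, and section 8.2 applies one attrition rate to both conditions. This stands. What is left is a permitted choice that the plan does not settle, not a declared biased comparison.

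A reader might also equate the control set with survey responders. Under section 6.1, a control participant can email or text a photo without taking the call, so the set may be wider. Section 4.1 ties sending to the call. Either way, control data still need action by the participant.

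The error rates might be read as what the trial should expect. They apply only to follow-up levels without baseline, the upper ones also need every non-responder to keep ordering, and D has no source in the plan. Sections 8.1 and 8.4.3 frame the outcome as a change, although the model in section 8.4 includes no baseline term. This objection stands and limits the claim about size.

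Finally, restricting to completers conditions on something that happens after the transition, and is not the only defensible choice. That is fair, and is why both sets should be reported.

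**Conclusion.** The concern holds as a gap in specification that can produce one-sided non-response selection in one secondary outcome. The differing data routes are explicit in sections 4.1 and 6.1, and nothing in sections 7.2, 8.3 or 8.4 keeps intervention non-responders out while their control counterparts are missing.

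The size is uncertain and probably modest. On follow-up levels at 20% attrition and the assumed gaps, the bias is about 0.04 to 0.10 SD (nominal 5% error becoming about 6.6% to 15%) if all non-responders still order, and about 0.02 to 0.06 SD (about 5.5% to 8%) if half do. For change from baseline a smaller effect is expected. Intervention records are selected too, since they require an order in the window, but on a different event from engaging with the study team.

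The primary outcome, food security, comes from the phone survey in both arms and is not affected. This is a cheap improvement, not a flaw that threatens the main result.

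**What to change.** In sections 8.3 and 8.4.3:

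1. Define the main analysis of this outcome as change from baseline in selections, compared between participants in both arms who have a baseline selection record and completed the follow-up survey.
2. Add a sensitivity analysis on all available records: every intervention order record, and control photos from participants who missed the call.
3. Within the intervention arm, compare selections of survey responders and non-responders. This sizes the non-response gap directly, which the control arm cannot do.
4. Report the availability of follow-up selections by arm, and for control by photo or recall.

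Reconcile sections 4.1 and 6.1 on how and when control participants send their selections.

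The cost is wording and extra analyses on data already planned. Setting aside up to about 39 intervention records widens the confidence interval by about 5%. The completer set still assumes that response depends on similar factors in both arms; items 2 to 4 help the reader judge that but do not remove it.
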